Appendix 6.	Pregnancy Precautions, Definition for Female of Childbearing Potential, and Contraceptive Requirements.....	119
Appendix 7.	Definitions of Stage 3 Opportunistic Illnesses in HIV	122

LIST OF IN-TEXT TABLES

Table 1-1.	GS-US-141-1218: Bictegravir Mean (%CV) PK Parameters Following Single Doses of bictegravir in Healthy Subjects (Bictegravir PK Analysis Set; Part A: Single Dosing).....	23
Table 1-2.	GS-US-141-1218: Bictegravir Plasma Pharmacokinetic Parameters by bictegravir Dose Following Multiple-Dose Administration of bictegravir (Analysis Set: Bictegravir PK Part B: Multiple-Dose)	23
Table 1-3.	GS-US-141-1218: Statistical Comparison of Bictegravir Pharmacokinetic Parameters Following Single-Dose Administration of Bictegravir in the Fasted and Fed States (Bictegravir PK Analysis Set).....	24
Table 1-4.	Trough Bictegravir Plasma Concentrations at Steady State Following Bictegravir Administration Under Fasting Conditions and Corresponding Protein-Adjusted IQ95 Values (Bictegravir PK Analysis Set)	25
Table 1-5.	GS-US-141-1475: Virologic Outcome at Week 48 Using the US FDA-Defined Snapshot Algorithm and HIV-1 RNA < 50 copies/mL (FAS)	28
Table 5-1.	Prior and Concomitant Medications	47

LIST OF IN-TEXT FIGURES

Figure 1-1.	GS-US-141-1219: Mean and 95% CIs of Change from Baseline in HIV-1 RNA (log ₁₀ copies/mL) (PP Analysis Set).....	26
Figure 6-1.	Virologic Rebound Schema.....	59

PROTOCOL SYNOPSIS

Gilead Sciences, Inc.
[name]
[name]

Study Title: A Phase 3, Randomized, Double-Blind Study to Evaluate the Safety and Efficacy of Fixed Dose Combination of Bictegravir/Emtricitabine/Tenofovir Alafenamide versus Dolutegravir + Emtricitabine/Tenofovir Disoproxil Fumarate in Treatment Naïve, HIV-1 and Hepatitis B Co-Infected Adults

IND Number: 125,589
EudraCT Number: 2018-000926-79
Clinical Trials.gov Identifier: NCT03547908

Study Centers Planned: Approximately 70 centers worldwide

Objectives: The primary objective of this study is:

- To evaluate the efficacy of fixed dose combination (FDC) of bictegravir /emtricitabine /tenofovir alafenamide (B/F/TAF) versus a regimen of dolutegravir (DTG) + emtricitabine/tenofovir disoproxil fumarate (F/TDF) in HIV and HBV treatment naïve, HIV-1 and HBV co-infected subjects as determined by the achievement of HIV-1 RNA < 50 copies/mL at Week 48
- To evaluate the efficacy of FDC of B/F/TAF versus DTG + F/TDF in HIV and HBV treatment naïve, HIV-1 and HBV co-infected subjects as determined by the proportion of subjects with plasma HBV DNA < 29 IU/mL at Week 48

The secondary objectives of this study are:

- To evaluate the efficacy of FDC of B/F/TAF versus DTG + F/TDF as determined by the achievement of HIV-1 RNA < 50 copies/mL at Week 96
- To evaluate the efficacy of FDC of B/F/TAF versus DTG + F/TDF as determined by the proportion of subjects with plasma HBV DNA < 29 IU/mL at Week 96

- To evaluate the efficacy of the FDC of B/F/TAF versus DTG + F/TDF as determined by the proportion of subjects with ALT normalization at Weeks 48 and 96
- To evaluate the efficacy of FDC of B/F/TAF versus DTG + F/TDF as determined by the proportion of subjects with HBsAg loss at Weeks 48 and 96
- To evaluate the safety and tolerability of the two treatment groups through Week 96

Study Design:

Randomized, double-blind, multicenter, active-controlled study to evaluate the safety and efficacy of a FDC of B/F/TAF versus DTG + F/TDF in HIV and HBV treatment-naïve, HIV-1 and HBV co-infected adult subjects. Subjects who provide written consent and meet all eligibility criteria will be randomized in a 1:1 ratio to one of the following two treatment groups:

Treatment Group 1 (n=120): FDC of bicitegravir

50 mg/emtricitabine 200 mg/ tenofovir alafenamide 25 mg (B/F/TAF) + placebo to match dolutegravir 50 mg and placebo to match FDC of emtricitabine 200 mg/tenofovir disoproxil fumarate 300 mg (F/TDF) administered orally, once daily, without regard to food

Treatment Group 2 (n=120): dolutegravir 50 mg (DTG) + FDC of emtricitabine 200 mg/TDF 300 mg (F/TDF) + placebo to match FDC of B/F/TAF administered orally, once daily, without regard to food

Randomization will be stratified by HBeAg (positive vs. negative), HBV DNA ($< 8 \log_{10}$ IU/mL vs. $\geq 8 \log_{10}$ IU/mL), CD4+ cell count (< 50 cells/ μ L vs. ≥ 50 cells/ μ L) at Screening

Number of Subjects Planned: Approximately 240 subjects

Target Population: Antiviral HIV-1 and HBV treatment-naïve, HIV-1 and HBV co-infected adults

Duration of Treatment: After screening, eligible subjects will be treated for at least 96 weeks during the blinded treatment phase. Following the Screening and Day 1 visits, subjects will be required to return for study visits at Weeks 4, 8, 12 and every 12 weeks thereafter.

Once all subjects complete their Week 96 visit and Gilead completes the Week 96 analysis, all subjects will return to the clinic (preferably within 30 days) for an End of Blinded Treatment Visit. At the End of Blinded Treatment Visit, if safety and efficacy of B/F/TAF FDC is demonstrated for the HIV-1 and HBV coinfecting subjects following

review of unblinded data, subjects in a country where B/F/TAF FDC is not available will be given the option to receive B/F/TAF FDC in an open label (OL) extension phase or until the product becomes accessible to subjects through an access program, or until Gilead Sciences elects to discontinue the study in that country, whichever occurs first.

All subjects participating in the OL extension phase, without regard to their blinded treatment regimen, will return for study visits at Week 12 OL and every 12 weeks thereafter.

Subjects who complete the study through the End of Blinded Treatment Visit and do not continue on the open-label extension phase, will be required to return to the clinic 30 days after the End of Blinded Treatment Visit for a 30-Day Follow-Up Visit.

Treatment assignments will be provided to the investigators within 30 days of the last subject completing the End of Blinded Treatment Visit.

Diagnosis and Main
Eligibility Criteria:

Subjects must meet ***all*** of the following inclusion criteria to be eligible to participate in the study.

- HIV-1 co-infection:
 - 1) Must be HIV antiretroviral treatment naïve with plasma HIV-1 RNA \geq 500 copies/mL at Screening
 - 2) \leq 10 days of prior therapy with any antiretroviral agent, including lamivudine, entecavir and approved or experimental integrase inhibitors following a diagnosis of HIV-1 infection (except the use for PrEP or PEP, up to one month prior to screening)
 - 3) Screening HIV-1 genotype report must show sensitivity to FTC (emtricitabine) and TFV (tenofovir).
- HBV co-infection:
 - 4) Must be HBV treatment naïve (defined as $<$ 12 weeks of oral antiviral treatment)
 - 5) Screening HBV DNA \geq 2,000 IU/mL
- Estimated glomerular filtration rate (eGFR) \geq 50 mL/min according to the Cockcroft-Gault (C-G) formula at the screening visit

Study Procedures/
Frequency:

After screening procedures, eligible subjects will be randomized 1:1 to Treatment Group 1 or Treatment Group 2 and treated for 96 weeks. Following the Day 1 visit, subjects will be required to return for study visits at Weeks 4, 8, and 12, and then every 12 weeks from Week 12

though Week 96. After Week 96, all subjects will continue to take their blinded study drugs and attend study visit every 12 weeks until the End of Blinded Treatment Visit.

Laboratory analyses (serum chemistry, liver function tests, hematology, urinalysis, pregnancy testing [for females of childbearing potential]), will be performed at the Screening, Day 1, and all subsequent study visits. HIV-1 RNA and CD4 + cell count will be performed at Screening, Day 1, and all subsequent study visits. HIV-1 genotype (RT and PR) will be determined at screening. Plasma HBV DNA levels, HBV serology (HBsAg and reflex anti-HBs Ab, and HBeAg and reflex anti-HBe Ab) will be performed at Screening, Day 1, and every 12 weeks thereafter. Plasma HBV DNA will be monitored at all study visits.

Serum samples for potential sequence analysis of HBV polymerase/reverse transcriptase (pol/RT) should be collected at all time points except screening. Sequencing analysis of the HBV pol/RT will be attempted for all viremic subjects (HBV DNA > 69 IU/mL) at Weeks 48, 96 or early study drug discontinuation as early as Week 8, as well as all subjects who meet virologic breakthrough criteria.

Trough PK blood sample will be obtained 20-28 hours following the last dose at Weeks 4, 12, and 36. Following an observed dose, one post-dose PK blood sample will be collected between 1 and 4 hours post-dose at Weeks 8 and 24.

Adverse events and concomitant medications will be assessed at each visit.

Test Product, Dose, and Mode of Administration:	FDC of bicitgravir 50 mg/emtricitabine 200 mg/tenofovir alafenamide 25 mg administered orally, once daily, without regard to food
--	---

Reference Therapy, Dose, and Mode of Administration:	dolutegravir 50mg + FDC of emtricitabine 200mg /tenofovir disoproxil fumarate 300mg administered orally, once daily, without regard to food
---	---

Criteria for Evaluation:

Safety:	Adverse events and clinical laboratory tests to evaluate the safety and tolerability of the treatment regimens.
---------	---

Efficacy:

The primary efficacy endpoints are:

- The proportion of subjects with HIV-1 RNA < 50 copies/mL at Week 48 as defined by the US Food and Drug Administration (FDA)-defined snapshot algorithm
- The proportion of subjects with plasma HBV DNA < 29 IU/mL at Week 48 by Missing = Failure approach

The secondary anti-HIV efficacy endpoints are:

- The proportion of subjects with HIV-1 RNA < 50 copies/mL at Week 96.
- The change from baseline in CD4 cell count and CD4% at Weeks 48 and 96

The secondary anti-HBV efficacy endpoints are:

- The proportion of subjects with plasma HBV DNA < 29 IU/mL at Week 96
- The proportion of subjects with ALT normalization at Weeks 48 and 96
- The proportion of subjects with HBsAg loss at Weeks 48 and 96

Pharmacokinetics:

Trough PK blood sample will be obtained 20-28 hours following the last dose at Weeks 4, 12, and 36. Following an observed dose, one post-dose PK blood sample will be collected between 1 and 4 hours post-dose at Weeks 8 and 24.

The plasma concentrations of bicitgravir, tenofovir alafenamide, and/or metabolites may be summarized using descriptive statistics.

CCI [REDACTED]

[REDACTED]

Statistical Methods:

The primary efficacy analysis will consist of a non-inferiority test of FDC of B/F/TAF versus DTG + F/TDF, with respect to the proportion of subjects who achieve HIV-1 RNA < 50 copies/mL at Week 48 as defined by the US FDA-defined snapshot algorithm. It will be concluded that B/F/TAF is non-inferior to DTG + F/TDF if the lower bound of the 2-sided 95% confidence interval (CI) of the difference (B/F/TAF – DTG + F/TDF) in the response rate (HIV-1 RNA < 50 copies/mL as defined by the US FDA-defined snapshot algorithm) is greater than -12%; ie, a margin of 12% is applied to non-inferiority assessment. The 95% CI will be constructed using a normal approximation method based on stratified Mantel-Haenszel proportions, where stratification factor includes baseline HIV-1 RNA ($\leq 100,000$ copies/mL vs. $> 100,000$ copies/mL).

The co-primary efficacy analysis will consist of a non-inferiority test of FDC of B/F/TAF versus DTG + F/TDF, with respect to the proportion of subjects with plasma HBV DNA < 29 IU/mL at Week 48 by Missing = Failure approach. It will be analyzed in a similar manner as described for the primary efficacy endpoint, except that the stratification factors include HBeAg status (positive vs. negative) and baseline HBV DNA ($< 8 \log_{10}$ IU/mL vs. $\geq 8 \log_{10}$ IU/mL).

To control type I error for the assessment of the primary and the co-primary efficacy endpoints, the hypothesis testing will be performed using the fallback procedure {[Wiens 2005](#)} in the sequential order with pre-specified 1-sided alpha level. The primary hypothesis of noninferiority of B/F/TAF relative to DTG + F/TDF, with respect to the proportion of subjects with HIV-1 RNA < 50 copies/mL at Week 48 (as defined by the FDA snapshot analysis) will be tested first. Non-inferiority test will be performed at one-sided, 0.025 alpha level. If non-inferiority is established, the co-primary hypothesis of noninferiority of B/F/TAF relative to DTG + F/TDF, with respect to the proportion of subjects with plasma HBV DNA < 29 IU/mL at Week 48 using Missing = Failure approach will be tested second at one-sided, 0.025 alpha level. Otherwise, the co-primary endpoint will not be tested at all.

The secondary anti-HIV efficacy endpoints include:

- 1) the proportion of subjects with HIV-1 RNA < 50 copies/mL at Week 96 as defined by the US FDA-defined snapshot algorithm, which will be analyzed in a similar manner as described for the primary efficacy endpoint.

- 2) the change from baseline in CD4 and CD4% at Weeks 48 and 96, which will be summarized by treatment using descriptive statistics. The differences and the associated 2-sided 95% CIs will be constructed using an Analysis of Variance (ANOVA) model, including treatment (B/F/TAF vs. DTG + F/TDF), HIV-1 RNA ($\leq 100,000$ copies/mL vs. $> 100,000$ copies/mL) as fixed effects in the model.

The secondary anti-HBV efficacy endpoints include:

- 1) the proportion of subjects with plasma HBV DNA < 29 IU/mL at Week 96
- 2) the proportion of subjects with ALT normalization at Weeks 48 and 96
- 3) the proportion of subjects with HBsAg loss at Weeks 48 and 96.

Each of these secondary anti-HBV efficacy endpoints will be analyzed in the same manner as described for the primary efficacy endpoint, except that stratification factors for the secondary efficacy endpoints include HBeAg status (positive vs. negative) and baseline HBV DNA ($< 8 \log_{10}$ IU/mL vs. $\geq 8 \log_{10}$ IU/mL).

The adverse events and clinical laboratory data will be summarized using descriptive statistics.

A total of approximately 240 HIV and HBV naïve, HIV-1 and HBV co-infected subjects, randomized in a 1:1 ratio to 2 treatment groups (120 subjects per treatment group), achieves 90% power to detect a non-inferiority margin of 12% in Week 48 response rate (HIV-1 RNA < 50 copies/mL as defined by the US FDA-defined snapshot algorithm) difference between the 2 treatment groups. For the sample size and power computation, it is assumed that both treatment groups have a response rate of 91% (based on Gilead Studies GS-US-380-1489 and GS-US-380-1490), that the non-inferiority margin is 12%, and that the significance level of the test is at a one-sided 0.025 level.

A total of approximately 240 subjects also provides 81% power to detect a non-inferiority margin of 12% with respect to the co-primary efficacy endpoint of the proportion of subjects with plasma HBV DNA < 29 IU/mL at Week 48. This assumes that both treatment groups have a response rate of 88% (based on Gilead Studies GS-US-320-0108 and GS-US-320-0110), that the non-inferiority margin is 12%, and that the significance level of the test is at a one-sided 0.025 level.

This study will be conducted in accordance with the guidelines of Good Clinical Practice (GCP) including archiving of essential documents.

GLOSSARY OF ABBREVIATIONS AND DEFINITION OF TERMS

° C	degrees Celsius
° F	degrees Fahrenheit
AE	adverse event
ALT	alanine aminotransferase
ANC	absolute neutrophil counts
ANOVA	Analysis of Variance
ARV	antiretroviral
AST	aspartate aminotransferase
AUC	area under the plasma/serum/peripheral blood mononuclear cell concentration versus time curve
BIC	bictegravir, B
B/F/TAF	bictegravir/emtricitabine/ tenofovir alafenamide, Bictarvy
BID	twice a day
BUN	blood urea nitrogen
CBC	complete blood count
CHB	chronic hepatitis B
CPT	Child-Pugh-Turcotte
CI	confidence interval
CL _{cr}	creatinine clearance
C _{max}	the maximum observed serum/plasma/peripheral blood mononuclear (PBMC) concentration of drug
CMH	Cochran-Mantel-Haenszel
CNS	central nervous system
COBI, /C	cobicistat
C _{tau}	the observed drug concentration at the end of the dosing interval
CPK	creatine phosphokinase
CRF	case report form(s)
CRO	contract (or clinical) research organization
CYP	cytochrome P450
DHHS	Department of Health and Human Services
DNA	deoxyribonucleic acid
DTG	dolutegravir, Tivicay®
ECG	electrocardiogram
eCRF	electronic case report form(s)
eGFR	estimated glomerular filtration rate
FAS	full analysis set
EVG	elvitegravir, E
E/C/F/TAF	elvitegravir/cobicistat/emtricitabine/tenofovir alafenamide, Genvoya®
E/C/F/TDF	elvitegravir/cobicistat/emtricitabine/tenofovir disoproxil fumarate, Stribild®
FAS	full analysis set
FDA	(United States) Food and Drug Administration

FDC	fixed dose combination
FTC/TAF	emtricitabine/tenofovir alafenamide , Descovy®
F/TDF	emtricitabine/tenofovir desoproxil fumarate, Truvada®
FSH	follicle-stimulating hormone
FTC, F	emtricitabine, Emtriva®
GCP	Good Clinical Practice (Guidelines)
GGT	gamma glutamyl transferase
GLSM	geometric least squares mean
GSI	Gilead Sciences, Inc.
GS-9883	bictegravir, B
GS-9883/F/TAF	GS-9883/emtricitabine/tenofovir alafenamide
HAART	highly active antiretroviral therapy
HBV	hepatitis B virus
HBcAb	hepatitis B core antibody
HBsAb	hepatitis B e-antibody
HBsAg	hepatitis B e-antigen
HBsAb	hepatitis B surface antibody
HBsAg	hepatitis B surface antigen
HCV	hepatitis C virus
HDPE	high-density polyethylene
HCC	hepatocellular carcinoma
hERG	human Ether-à-go-go-Related Gene
HIV	human immunodeficiency virus
HIV Sx	HIV Symptoms Distress Module
HLA	human leukocyte antigen
IB	investigator's brochure
ICH	International Conference on Harmonisation
IDMC	Independent Data Monitoring Committee
IMP	Investigational Medicinal Product
IND	Investigational New Drug (Application)
INSTI	integrase strand-transfer inhibitors
IRB	institutional review board
IWRS	interactive web response system
KS	Kaposi's sarcoma
LDH	lactate dehydrogenase
LLN	lower limit of the normal range
MedDRA	Medical Dictionary for Regulatory Activities
mg	milligram
MH	Mantel-Haenszel
min	minute

mmHg	millimeters mercury
nM	nanoMolar
NNRTI	non-nucleoside reverse transcriptase inhibitor
NOEL	no observed effect level
OL	Open Label
NOAEL	no observed adverse effect level
NRTI	nucleoside/nucleotide reverse transcriptase inhibitor
PEP	post-exposure prophylaxis
P-gp	P-glycoprotein
PI	protease inhibitor
PK	Pharmacokinetic
PT	preferred term
PT	prothrombin time
PTM	placebo-to-match
PVE	Pharmacovigilance and Epidemiology
QD	once daily
RAL	raltegravir
RNA	ribonucleic acid
SA	single agent
SAE	serious adverse event
SmPC	Summary of Product Characteristics
SUSAR	Suspected Unexpected Serious Adverse Reaction
TAF	tenofovir alafenamide
TDF	tenofovir disoproxil fumarate, Viread®
TFV-DP	tenofovir diphosphate (TFVpp)
t_{\max}	the time (observed time point) of C_{\max}
TSH	thyroid stimulating hormone
UGT1A1	uridine 5'-diphospho-glucuronosyltransferase
UGT	uridine glucuronosyltransferase
ULN	upper limit of the normal range
US	United States

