1. INTRODUCTION

1.1. Background

There is an urgent need to address HIV and HBV coinfection worldwide. Both HIV and HBV infection can lead to chronic disease, with attendant morbidity and mortality that is synergistically exacerbated by coinfection with both viruses.

Over 2 billion people are infected, 400 million chronically with Hepatitis B Virus, (HBV), which is a primary cause of chronic liver disease and a major contributor to mortality, contributing to half the burden of cirrhosis and hepatocellular carcinoma (HCC). HBV is endemic in parts of Asia and Africa, with 70% of the population showing serologic evidence of current or prior infection and approximately 8-15% with chronic hepatitis B infection {[Kalayjian 2003](#)}, {[Drake 2004](#)}, {[Kourtis 2012](#)}.

There are estimated to be 35 million people living with HIV/AIDS, with the majority in Asia and Africa; estimates ranging for a total of approximately 3-6 million individuals coinfecting with HIV and HBV, coinfection rates are as high as 25% in areas where both viruses are endemic {[Kourtis 2012](#)}.

Coinfection worsens morbidity and mortality synergistically; HIV-HBV coinfecting patients have higher HBV DNA levels and progress to chronic hepatitis B five times more quickly than HBV mono-infected patients and have higher risk of cirrhosis and HCC.

In HIV-positive patients co-infected with HBV, F/TDF or F/TAF are the preferred NRTI backbone of a fully suppressive antiretroviral regimen {[Panel on Antiretroviral Guidelines for Adults and Adolescents 2016](#)}. For the majority of mono-infected chronic hepatitis B (CHB) subjects, life-long treatment is required as only a small percentage (< 10%) of subjects experience sustained loss of hepatitis B surface antigen (HBsAg), and as a consequence, achieve an effective cure of the disease. However, data in HIV/HBV coinfecting patients are limited {[Charpentier 2015](#)}.

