8.5.2.2. Secondary anti-HBV Efficacy Analysis

The secondary anti-HBV efficacy endpoints include: (1) the proportion of subjects with HBV DNA < 29 copies/mL at Week 96, (2) the proportion of subjects with ALT normalization (i.e., subjects had ALT > ULN at baseline and a ALT ≤ ULN at the given post-baseline) at Weeks 48 and 96, and (3) the proportion of subjects with HBsAg loss at Weeks 48 and 96.

All these three anti-HBV efficacy endpoints will be analyzed using both Missing = Failure and Missing = Excluded approach. The 95% CIs will be constructed in the similar manner as described for the primary efficacy endpoint with stratification factors of HBeAg status (positive vs. negative) and baseline HBV DNA (< 8 log₁₀ IU/mL vs. ≥ 8 log₁₀ IU/mL).

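### The synopsis, read literally, applies the -12% non-inferiority rule to HBsAg loss, while section 8.5.2.2 carries over only the confidence interval; on a rare outcome that rule cannot show that any effect is preserved

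*Protocol*

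**What the plan says.** The Statistical Methods part of the protocol synopsis defines the primary analysis as a non-inferiority test of HIV-1 RNA response. The criterion is that the lower limit of the two-sided 95% interval for the difference, B/F/TAF minus DTG + F/TDF, "is greater than -12%; ie, a margin of 12% is applied to non-inferiority assessment". The interval is a normal approximation on stratified Mantel-Haenszel proportions.

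The synopsis then lists three secondary anti-HBV endpoints, the third being "the proportion of subjects with HBsAg loss at Weeks 48 and 96". It continues: "Each of these secondary anti-HBV efficacy endpoints will be analyzed in the same manner as described for the primary efficacy endpoint". The only stated exception is that the strata are HBeAg status and baseline HBV DNA.

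Protocol section 8.5.2.2 covers the same three endpoints in narrower terms: "The 95% CIs will be constructed in the similar manner as described for the primary efficacy endpoint with stratification factors" of HBeAg status and baseline HBV DNA. It adds that "All these three anti-HBV efficacy endpoints will be analyzed using both Missing = Failure and Missing = Excluded approach". It states no hypothesis, margin or non-inferiority conclusion for HBsAg loss.

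The only HBsAg-loss rate in either document is in protocol section 1.1. For mono-infected chronic hepatitis B it says "only a small percentage (< 10%) of subjects experience sustained loss of hepatitis B surface antigen (HBsAg"). It gives no time point and notes that data in co-infected patients are limited.

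The supplied SAP covers the final analysis. Its sections 6 and 6.2.1.2 refer the Week 48 and Week 96 secondary analyses to earlier SAPs. Its section 3.5 confines alpha adjustment to the primary endpoints at Week 48.

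**The concern.** An absolute margin of 12 points means something when about nine in ten subjects respond. It means little when few do. A proportion cannot fall below zero, so if the control rate is under 12% the null hypothesis that B/F/TAF is at least 12 points worse cannot be true, and passing the rule refutes nothing.

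HBsAg loss is a named secondary objective. Under the literal synopsis wording, a report could call B/F/TAF non-inferior for HBsAg loss when no subject on B/F/TAF had lost HBsAg. What is at stake is that sentence in a report, not the trial's primary conclusions.

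**Working it through.** **Inputs.** From the protocol: 120 per arm (synopsis and section 8.8), margin 12 points, two-sided 95% interval, and assumed response rates of 91% (HIV-1 RNA) and 88% (HBV DNA). The control rate of HBsAg loss is not given, so the range 2% to 10% is my assumption.

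**1. The plan's own power figures.** Power = Φ(0.12/SE − 1.96), with SE = √(2p(1−p)/120).

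- p = 0.91: SE = 0.0369; 0.12/0.0369 − 1.96 = 1.288; power 90.1% (stated 90%).
- p = 0.88: SE = 0.0420; 0.12/0.0420 − 1.96 = 0.900; power 81.6% (stated 81%).

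Both reproduce, so the rule is being read as the plan uses it.

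**2. How the rule behaves where it was planned.** By exact enumeration of two binomials with n = 120 and an unstratified interval, a true deficit of exactly 12 points passes in 2.8% of trials for HIV (79% against 91%) and 2.7% for HBV DNA (76% against 88%). Both are close to the nominal 2.5%.

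**3. The same rule with no HBsAg loss on B/F/TAF.** With 0/120 against x/120 and q = x/120, the lower limit is −q − 1.96·√(q(1−q)/120).

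- x = 8: −0.0667 − 1.96 × 0.02277 = −0.111. Passes.
- x = 9: −0.0750 − 1.96 × 0.02404 = −0.122. Fails.

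The cut-off of 8 is unchanged by a continuity correction or an n−1 variance. With fewer evaluable subjects it is 7 of 110 or 6 of 100.

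**4. Chance of declaring non-inferiority when the true B/F/TAF rate is 0%.** This is P(X ≤ 8) for X binomial with n = 120 and the control rate.

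| Assumed control rate | Declared non-inferior |
|---|---|
| 2% | 99.9% |
| 3% | 99.0% |
| 5% | 85.3% |
| 7% | 53.5% |
| 8% | 37.1% |
| 10% | 14.1% |

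The probability is 90% at a control rate of about 4.6%, 80% at about 5.4% and 50% at about 7.2%.

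**5. Stratified version.** A simulated four-stratum Mantel-Haenszel interval, with assumed stratum shares, gives slightly higher values: about 87% at 5%, 56–58% at 7%, 40–42% at 8% and 17–18% at 9.9%.

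**6. Half the control rate on B/F/TAF.** By exact enumeration, non-inferiority is declared in 95% of trials at a control rate of 5%, 83% at 7% and 56% at 10%.

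**The case against.** The strongest reply is that section 8.5.2.2 is the detailed methods section, and there "The 95% CIs will be constructed in the similar manner as described for the primary efficacy endpoint" is all that is carried over. Section 8.5.2.1, by contrast, applies the primary endpoint's method to Week 96 HIV-1 RNA, and hypotheses with a 12% margin are written out only for the two primary endpoints (sections 8.5.1.2 and 8.5.1.3). On this reading no -12% test of HBsAg loss was ever intended. Much of that stands, and the documents do not show that the rule was applied. It does not remove the conflict. The synopsis names one exception, the strata, and it uses similar wording for the co-primary HBV DNA endpoint, where the margin plainly does carry over. For CD4, where it wants no such test, it specifies descriptive statistics and model-based intervals.

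Two stronger readings are tempting, and the documents support neither.

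- A reader might infer that the rule usually passes whenever HBsAg loss is below 10%. It does so only below about 7.2%. Above that the width of the interval takes the lower limit past -12% more often than not.
- A reader might treat the section 1.1 figure as this trial's expected rate, or treat the endpoint as cure. The figure is for sustained loss in mono-infected patients with no time point, and sustained loss is what section 1.1 links to cure. The endpoint here is loss at Weeks 48 and 96.

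It is also fair to say that the counts and interval, if reported, would show a zero in the B/F/TAF arm.

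**Conclusion.** The synopsis and section 8.5.2.2 differ on what is done with HBsAg loss, and the synopsis version would allow a conclusion with no content. The structural point needs one assumption, a control rate below 12%: total absence of effect then sits inside the margin, so a pass cannot show that any effect is preserved.

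How often an uninformative pass would occur depends on a rate that the documents do not give. At control rates of 5% or less it is at least about 85% of trials with no loss on B/F/TAF. At 8% it is 37% and at 10% it is 14%. These figures assume 120 evaluable subjects per arm and an unstratified interval; stratification raises them slightly.

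The priority is low. The endpoint is secondary and lies outside the alpha-controlled hypotheses. SAP section 6 says the Week 48 and Week 96 analyses are done, under SAPs that may already restrict HBsAg loss to estimation.

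**What to change.** Align the synopsis with section 8.5.2.2, and state in both that the -12% rule does not apply to HBsAg loss at Week 48 or Week 96. Report the number and proportion with loss in each arm, the difference and its 95% interval, as description only. An interval suited to rare events is preferable to the normal approximation.

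Draw no superiority conclusion either. With the unstratified normal-approximation interval, 4/120 on B/F/TAF against 0/120 gives a lower limit of 0.0333 − 1.96 × 0.0164 = +0.1%, which excludes zero, while a two-sided Fisher test gives p of about 0.12, and no alpha is allocated to this endpoint.

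Since the analyses have been run, the practical step is to check the Week 48 and Week 96 SAPs and reports for any non-inferiority statement on HBsAg loss, and to remove or qualify it. The cost is about one sentence in each place. The tables stay the same apart from the interval method, and the only thing given up is a statement that carried no information.
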